Specific Aim 3: Conduct a pilot randomized controlled trial of the brief, Veteran-targeted PCI in a sample of recent Veterans with stress-related mental health disorders (n=48) to assess feasibility and preliminary efficacy.

Hypothesis 3a: The brief PCI will be shown to be feasible as evidenced by successful rates of recruitment, attendance at intervention sessions by Veterans, and interventionist fidelity to the intervention.

Hypothesis 3b: Compared to a health and wellness control intervention, participation in the brief, Veteran targeted PCI will result in significant increases in (1) Veteran PCC behaviors in mental health care encounters and (2) functioning in domains of health, purpose, and community.

Secondary analysis: Comparing the RCT arms, explore (1) Veteran attrition from VA mental health care via chart review and (2) Veteran self-assessment of levels of clinical symptomology with the DASS-21, AUDIT, DAST 10, and PCL-5.

2 * Discuss the research design including but not limited to such issues as: probability of group assignment, potential for subject to be randomized to placebo group, use of control subjects, etc.:

Aim 1: 35 recent Veterans with stress-related mental health disorders and their VA mental health providers will consent to audio-recording of one treatment encounter. (There is no randomization or group assignment.)

Aim 2: Two focus groups of 4-6 Veterans each will be held. We will also conduct a clinical demonstration of the PCI with 10 Veterans to examine acceptability and further refine the intervention. Participants will complete the three session intervention and participate in a qualitative interview about their experience. (There is no randomization or group assignment.)

Aim 3: We will conduct a pilot randomized controlled trial of the PCI (n=48) to assess feasibility and preliminary efficacy. 24 participants will be randomized to a health and wellness control condition and 24 to the experimental treatment condition.

3 * Describe the relevant prior experience and gaps in current knowledge. Describe any relevant preliminary data:

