The primary goal of the Aim 3 pilot RCT is to assess the feasibility of PCI for a larger confirmatory RCT. After considering time and resources available with this CDA-2, we believe it will be feasible to randomize 24 individuals per condition. We expect 20% of those randomized in each condition will miss data collection at TP3, and 30% at TP4. This sample size will not be sufficient to detect "small" clinically important differences at TP3 (post-treatment) with 80% power as would be expected of a larger confirmatory RCT. However, with the anticipated 19 participants per condition with complete data at TP3, power is estimated to be equal to .80 for detecting between "medium" and "large" effect sizes ($d=.65$) with the ANCOVA analysis, assuming TP1 to TP3 or TP4 correlation in the response variable is $r=0.7$.

2 * Provide the plan for data analysis. Include in the description the types of comparisons that are planned (e.g., comparison of means, comparison of proportions, regressions, analysis of variance, etc.), which is the primary comparison/analysis, and how the analyses proposed will relate to the primary purposes of the study:

Aim 1 data analysis.

Audio recordings of Aim 1 will not be transcribed as outlined in Aim 2. Recorded Veteran-provider encounters will be coded by research staff using the Measure of Patient-Centered Communication (MPCC). Theoretically grounded in Stewart et al.'s model of patient-centered care, the MPCC is a method for trained raters to assess and quantify recordings of patient-provider encounters. It does not necessitate that the recorded encounters be transcribed for coding. The MPCC has been used to code many types of patient/provider encounters including care for acute and chronic conditions, routine physicals, follow-up visits and emergency department encounters.

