Aim 3, hypothesis 3b. We hypothesize that compared to control participants, participation in the brief, Veteran-focused, PCI will result in significantly greater increase in (1) Veteran PCC behaviors in mental health care encounters as measured by the MPCC and (2) functioning in domains of health, purpose, and community as measured by the VR-36 and WHODASS. Our overall approach will be to compare group means using a mixed model, accounting for common providers among participants with a random provider effect. If

an out of balance prognostic covariate is found in baseline comparisons this variable will also be included in the model, although the number of covariates that can be adjusted for will be limited by the sample size. We chose to use mixed models versus GEE (generalized estimating equations) to avoid bias due to unequal cluster sizes or sample size.

More specifically, for hypothesis 3b(1) to compare the treatment arms on PCC behaviors in mental health care encounters we will use the MPCC, assessed only at time point 2. The independent variable will be the treatment group indicator. For hypothesis 3b(2) to examine whether relative to control the treatment group has greater functioning (subscales of the VR-36 and WHODAS), we will compare group means at time points 3 and 4 using a linear mixed model ANCOVA. The comparison at time point 3 will be primary and at time point 4,

secondary. For this hypothesis, after adjustment for baseline, there will be 2 repeated measures (time points 3 and 4) which will be assumed to be correlated (i.e. thru correlated error terms). However, contrasts will be specified in order to compare the groups at time point 3, separately from time point 4.

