Aim 3, secondary and exploratory analyses. Secondary preliminary efficacy outcomes in the treatment group are (1) Veteran attrition from VA mental health care as compared to the control participants as established via chart review at TP3 and TP4 and (2) levels of Veteran self-assessment of clinical symptomology with the DASS-21, AUDIT, DAST 10, and PCL-5 at time points 1, 3, and 4. For (1) we will determine the proportion of scheduled mental health care appointments that participants did not attend or canceled between TP1 and TP3 and TP3 and TP4, via chart review for the treatment and control groups. Proportions rather than raw counts will be analyzed to account for different patients having different numbers of scheduled appointments. If the number of different values for the proportions is few (say less than five), we will either define ordinal categories or dichotomize the proportions as there may be a lot zeros. We would then use a logit mixed model ANCOVA. If there are more than five unique values, but the distribution has substantial skew, we will again use an ordinal logit mixed model. Otherwise, if the distribution is close to symmetric we will use a linear mixed model ANCOVA. In either case we will use semi-parametric 'sandwich' standard errors known for their robustness to deviation from model assumptions. For (2), the self-assessment symptom measures will be analyzed to assess clinically significant change. Due to the heterogeneity of the inclusion diagnoses this may involve forming subgroups based on baseline symptom severity, and therefore these analyses will be exploratory due to the small sample size. Additionally, we will form z-scores for each symptom measure and pool scores across symptom type as it is expected that all participants will have significant severity on at least one symptom measure. The DASS-21 and DAST 10 scores map onto five clinically meaningful levels and the AUDIT score maps onto four clinically meaningful levels. A mixed effects ordered logit model will be used to account for the ordinal levels of the response variable and will include random provider effect. A 10 point change on the PCL-5 has been established as clinically significant, hence, binary indicator variables will be constructed to indicate 10-point improvement (or not) at both TP3 and TP4. A mixed effects logistic regression model with random provider effect will be used to compare probability of 10-point improvement between the two groups.

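### No symptom scale is compared between arms on its own raw score; for the PCL-5, the 10-point yes/no gives up roughly 30–50% of the power of the plan's own ANCOVA

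*Combined protocol and SAP*

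**What the plan says.** Under Sample Size and Data Analysis, item 2 (Aim 3, secondary and exploratory analyses), three scales are reduced to ordered levels: "The DASS-21 and DAST 10 scores map onto five clinically meaningful levels and the AUDIT score maps onto four clinically meaningful levels". For these, "A mixed effects ordered logit model will be used to account for the ordinal levels of the response variable", with a random provider effect. For the PCL-5, "binary indicator variables will be constructed to indicate 10-point improvement (or not) at both TP3 and TP4", compared by mixed logistic regression. The section also plans z-scores pooled across symptom types, but gives no model for them. It states that the symptom measures are there to assess clinically significant change, and it calls the analyses exploratory because the sample is small.

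Functioning is handled differently. Under Aim 3, hypothesis 3b, "we will compare group means at time points 3 and 4 using a linear mixed model ANCOVA", adjusted for baseline, with separate contrasts at TP3 (primary) and TP4 (secondary). The power statement in item 1 also refers to an ANCOVA: "with the anticipated 19 participants per condition with complete data at TP3, power is estimated to be equal to .80", for "effect sizes ($d=.65$) with the ANCOVA analysis" and a baseline to follow-up correlation of 0.7.

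**The concern.** The plan uses scores as scores for functioning, but no single symptom scale gets that treatment. Movement that does not cross a band edge or the 10-point line does not count. The plan's rule for missed appointments is to use categories only when there are few distinct values or marked skew, and a linear ANCOVA otherwise. The symptom scales are categorised with no such check.

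The pooled z-score does not fill the gap. It cannot show which symptom moved, and an effect confined to one scale is diluted by the others.

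Two things are at stake. With about 19 per arm, a real effect on one scale is more likely to be missed. The pilot is also meant to inform a larger confirmatory trial, which would usually be planned from a mean difference and an SD per scale. Band odds ratios and responder rates do not supply these.

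**Working it through.** **Inputs from the plan.** Allocation: "24 participants will be randomized to a health and wellness control condition and 24 to the experimental treatment condition". Missing data: "We expect 20% of those randomized in each condition will miss data collection at TP3, and 30% at TP4", so 24 × 0.8 = 19.2 per arm at TP3 and 24 × 0.7 = 16.8 at TP4. The plan uses 19 per arm, d = .65 and r = .7.

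**Assumptions not in the plan.** Two-sided alpha .05, normally distributed scores, PCL-5 SD of 10–20 points, control-arm improvement m of 0–10 points, and the share of Veterans in each band. The .65 SD effect is carried over to the symptom scales; the plan states no effect size for them. Provider clustering is ignored.

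**1. The plan's own figure.** SE = √(2/19) × √(1 − 0.7²) = 0.3244 × 0.7141 = 0.2317 SD units. Then 0.65/0.2317 = 2.805, and power = Φ(2.805 − 1.96) = .80, as stated. A noncentral t with 35 df gives .78.

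**2. PCL-5 as a 10-point yes/no.** The SD of change is √(2 − 2 × 0.7) = 0.775 SD units. The chance of a 10-point improvement is Φ[(m/SD + δ − 10/SD)/0.775], with δ = 0 in control and .65 in treatment. Power is Φ[(p₁ − p₀ − 1.96·SE₀)/SE₁], where SE₀ uses the pooled proportion and SE₁ the separate ones.

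Worked case, SD 10 and m = 0: p₀ = Φ(−1.291) = .098 and p₁ = Φ(−0.452) = .326. SE₀ = .1326 and SE₁ = .1274. Power = Φ[(.228 − .260)/.1274] = Φ(−0.25) = .40.

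| PCL-5 SD | m | Control | Treatment | Power |
|---|---|---|---|---|
| 10 | 0 | 9.8% | 32.6% | .40 |
| 15 | 0 | 19.5% | 49.1% | .49 |
| 15 | 5 | 33.3% | 65.9% | .52 |
| 20 | 0 | 25.9% | 57.7% | .51 |
| any | 10 | 50.0% | 79.9% | .49 |

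Against .80, the loss is 1 − .40/.80 = 50% to 1 − .52/.80 = 35%. Simulating the two-proportion test gives .41–.54; at the top, 1 − .54/.78 = 31%.

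The size depends on the test. In 2,248 simulated trials (raw ANCOVA power .757):

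| Scenario | Likelihood ratio | Wald | Fisher |
|---|---|---|---|
| SD 12, m = 0 | .458 | .375 | .327 |
| SD 15, m = 5 | .589 | .473 | .423 |
| SD 20, m = 0 | .565 | .485 | .413 |

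Over all scenarios run, the relative loss was 19–39% (likelihood ratio), 36–50% (Wald) and 43–57% (Fisher).

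**3. Banded scales, same simulation.** These are likelihood-ratio tests from an ordered logit.

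| Bands | Baseline in model | No baseline |
|---|---|---|
| Five, even | .703 (loss 7%) | .473 (38%) |
| Five, 40/20/20/15/5 | .638 (16%) | .419 (45%) |
| Four, even | .678 (10%) | .458 (40%) |

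Over all runs, the loss with baseline kept was 7–17%. The right-hand column is mostly the price of dropping baseline: a raw score without baseline also falls to Φ(0.65/0.3244 − 1.96) = .52, a 35% loss.

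**4. Most Veterans in the lowest band.** With 65–70% there and baseline kept, banded power is .49 (four bands) and .45 (five bands), a loss of 36–40% against an ideal normal score. But a scale with that pile-up is likely to have a floor in its raw total too. With a floor inside the lowest band, raw ANCOVA falls to .58 and .54. The result depends on how many of that band sit at the floor (assumed shares; 4,000 runs for raw, 500 per banding for the ordered logit):

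| Share in lowest band | Raw ANCOVA with 50/70/90% of that band at the floor | Ordered logit, banded baseline |
|---|---|---|
| 60% | .61 / .52 / .42 | .52 |
| 75% | .55 / .43 / .28 | .36 |

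The raw score is ahead, level or behind according to the floor.

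**The case against.** The strongest reply is that the plan asks a different question. It wants clinically significant change, and it chose levels and a threshold that it regards as clinically meaningful. Replacing those analyses with mean differences would change the question. That stands, and it is why the raw-score analysis should be an addition.

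Second, these outcomes are secondary, labelled exploratory, and sit in a pilot whose main goal is feasibility. The plan concedes that small effects cannot be detected, and its .80 was not claimed for symptom scales. No decision rule depends on them. That also stands and limits the importance of the point.

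Third, the pooled z-score retains continuous information and suits a mixed-diagnosis sample in which any one scale may be irrelevant to many participants. This is fair as far as it goes, but it gives no result per scale.

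A reader might infer that categorising costs a third to a half of the power on all four scales. The plan does not support that. For the DASS-21, DAST 10 and AUDIT, a loss of that size needs either no baseline term or a heavy pile-up in the lowest band. The ordered-logit text names only a provider effect, so the first is a literal reading, but that loss comes mainly from the missing covariate and not from banding. In the second case the fair comparator is a raw score with its own floor, which also loses power. The plan gives no band occupancy from which to settle this.

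**Conclusion.** The point holds in a limited form. No single symptom scale is compared on its raw score. For the PCL-5 the cost is material: about .40–.54 against .78–.80, a relative loss of roughly 30–50% by a two-proportion test and 19–39% by a likelihood-ratio test. For reasonably filled bands with baseline kept, the cost is about 7–17%. For alcohol and drug scores concentrated in the lowest band, the advantage of a raw score may be small, nil or reversed.

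The figures rest on the plan's 19 per arm, d = .65 and r = .7, and on the assumptions listed in the working. They apply to TP3; with about 17 per arm at TP4, power would be lower for either approach. Because the outcomes are exploratory, this is an inexpensive improvement to the plan and not a flaw in its main inference.

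**What to change.** Add to the secondary and exploratory analyses a baseline-adjusted linear mixed ANCOVA of each raw total (PCL-5, DASS-21, DAST 10 and alcohol score), with a random provider effect and the TP3 and TP4 contrasts already defined for hypothesis 3b. Report the adjusted mean difference with its confidence interval and the SD. The PCL-5 and DASS-21 matter most.

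Keep the ordered-logit and 10-point analyses as the clinically-significant-change analyses, and keep every symptom analysis labelled exploratory.

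The cost is SAP wording: the data are already collected and the model is already in use for functioning. The downsides are a few more exploratory comparisons and, for skewed alcohol and drug scores, a residual check with a transformation or the robust standard errors that the plan already uses for missed appointments.

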Aim 2 clinical demonstration of the PCI. The final task in Aim 2 will be to complete a clinical demonstration of the PCI (in its form after Meeting 3 input is incorporated) to examine acceptability using qualitative interviews. Participants will be 10 recent Veterans with current stress-related mental health diagnoses. The interventionist will be the same interventionist who will deliver the PCI in Aim 3. The

purpose of the clinical demonstration is to identify PCI features or materials that appear functional in theory but do not execute well in a clinical setting. At the end of their participation in the clinical demonstration, each Veteran will complete a qualitative semi-structured interview that will discuss their experience with the PCI and their thoughts about its overall utility. The interview will ask for feedback about the PCI content, materials, scheduling, and experience. This will include review of the format and content of the sessions, handouts, and educational materials. Questions will focus on the participants' reactions to the content, including utility and clarity. Interviews will begin with broad open questions about initial reactions, explore those thoroughly, and subsequently ask specific follow up questions to elicit information about each facet of the intervention. After each interview the interviewer will append a field note documenting pertinent observations. Interviews will be in-person and recorded for verbatim transcription to facilitate coding.

Aim 2 analysis of semi-structured interviews. We will use qualitative RAP to analyze the semi-structured interviews. RAP is ideal for PAR studies with action-oriented goals: it uses team-based coding and focuses data analysis in order to answers to specific research questions.

Aim 3 data analysis.

First, summary statistics of demographic, clinical, and baseline outcome scale scores will be calculated for the total sample and compared between treatment groups to check the success of the randomization and for outliers. If there is an out-of-balance variable that is plausibly a prognostic factor for PCI outcome, we will adjust for this variable when comparing the two treatment arms. Nesting of multiple patients within the same provider will be identified.

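### The ordered-logit models for the DASS-21, DAST 10 and AUDIT bands do not name the TP1 score as a covariate, which leaves precision unused; the alcohol instrument also needs reconciling

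*Combined protocol and SAP*

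**What the plan says.** All analysis text is in Sample Size and Data Analysis, question 2.

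- **Symptom outcomes (Aim 3, secondary and exploratory analyses).** The second secondary outcome is "levels of Veteran self-assessment of clinical symptomology with the DASS-21, AUDIT, DAST 10, and PCL-5 at time points 1, 3, and 4", so a TP1 score exists for every measure. The DASS-21 and DAST 10 are cut into five bands, and "the AUDIT score maps onto four clinically meaningful levels". The model for the bands will "account for the ordinal levels of the response variable and will include random provider effect". No other term is named. The same paragraph says "we will form z-scores for each symptom measure and pool scores across symptom type", with no model for the result, and handles the PCL-5 through a 10-point improvement flag. On status it says "therefore these analyses will be exploratory due to the small sample size".
- **Functioning outcomes (Aim 3, hypothesis 3b).** Here baseline is explicit: "after adjustment for baseline, there will be 2 repeated measures (time points 3 and 4").
- **Covariate rule (Aim 3 data analysis).** At the start, "summary statistics of demographic, clinical, and baseline outcome scale scores will be calculated for the total sample and compared between treatment groups". Then: "If there is an out-of-balance variable that is plausibly a prognostic factor for PCI outcome, we will adjust for this variable". Hypothesis 3b repeats the rule and warns that the sample size restricts how many covariates can be used.
- **Instrument.** The objectives and the analysis text name AUDIT. Both lists under Surveys/Questionnaires, including the one for RCT participants, give the AUDIT-C, and it is the only alcohol form among the uploads.

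**The concern.** With about 38 participants at TP3, the baseline value of the outcome is usually the most useful covariate available. The plan uses it for functioning but does not name it for the symptom bands. The imbalance rule does not fill the gap: it acts only if the arms happen to differ at baseline, whereas the precision gain from a prognostic baseline score is there even when they do not.

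The paragraph also aims to assess change, yet a model of TP3 and TP4 bands with no TP1 term compares levels. As written, it allows at least three analyses: TP1 left out, TP1 as a covariate, or TP1 as a further repeated response. They differ in power, and leaving the choice open means it could be made after the data are seen. The pooled z-score has the same gap, because no model is stated for it.

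For alcohol, the four-band analysis names an instrument that the RCT questionnaire list does not contain.

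**Working it through.** **Inputs.** From the sample size rationale: 24 randomised per arm, 20% missing at TP3 (24 × 0.8 = 19.2, so 19 per arm), d = .65, r = .7 and power .80. Assumed: two-sided .05 (the power statement gives neither level nor sidedness); that d = .65 carries over to symptom scores; r from .3 to .7; and the band shapes shown below. The documents give none of these for symptom scales.

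**1. The plan's own figure.** Residual SD after baseline adjustment = √(1 − 0.7²) = 0.714. Then 0.65 / (0.714 × √(2/19)) = 2.805, and Φ(2.805 − 1.960) = .80. The stated power reproduces. Without baseline, 0.65 / √(2/19) = 2.003 and Φ(2.003 − 1.960) = .52. So the .80 depends on baseline adjustment, which the functioning model has.

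**2. One continuous score (a stand-in for the pooled z-score).** Noncentral t, 19 per arm. The SD is 1 for TP3 only, √(2(1 − r)) for a change score and √(1 − r²) for ANCOVA.

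| r | TP3 only | Change score | ANCOVA |
|---|---|---|---|
| .3 | .496 | .378 | .533 |
| .5 | .496 | .496 | .614 |
| .7 | .496 | .711 | .779 |

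Over the better alternative, ANCOVA gains about 4, 12 and 7 points.

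**3. Ordered bands.** Simulation: TP1 and TP3 latent normal with correlation r; TP3 shifted by .65 in one arm; bands cut on the baseline distribution; proportional-odds likelihood-ratio test. Each cell shows power without v with the TP1 covariate. The equal-size column sets the critical value from null runs, so both tests have the same type I error.

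| Bands | r | Nominal test | Equal size | Gain at equal size |
|---|---|---|---|---|
| Five equal | .3 | .470 v .503 | .439 v .456 | 1.7 |
| Four equal | .3 | .457 v .487 | .432 v .446 | 1.4 |
| Five equal | .5 | .472 v .571 | .452 v .524 | 7.2 |
| Four equal | .5 | .456 v .548 | .430 v .501 | 7.1 |
| Five, 60% in lowest | .5 | .355 v .429 | .349 v .395 | 4.6 |
| Four, 60% in lowest | .5 | .354 v .426 | .348 v .387 | 3.9 |
| Five equal, provider effect fitted | .5 | .487 v .575 | .444 v .480 | 3.6 |
| Five equal | .7 | .469 v .708 | .443 v .662 | 21.9 |
| Four equal | .7 | .456 v .679 | .432 v .630 | 19.8 |
| Five, 60% in lowest | .7 | .357 v .527 | .337 v .474 | 13.7 |
| Four, 60% in lowest | .7 | .354 v .525 | .324 v .451 | 12.7 |
| Five equal, provider effect fitted | .7 | .497 v .725 | .514 v .697 | 18.3 |

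Equal-band rows use 20,000 runs. Skewed rows use 12,000, except four bands at r = .7 (4,000). The provider rows assume 12 providers carrying 10% of the variance and rest on 1,038 runs (r = .5) and 1,111 runs (r = .7), so they are less precise.

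**4. Type I error of the nominal test.** It is .062 to .072 with the covariate and .053 to .059 without. With the provider effect fitted at r = .5, it is .084 v .063. That run is closest to the model the plan names; its Monte Carlo standard error is √(.084 × .916 / 1,038) ≈ .009.

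**5. TP1 as a repeated response.** With a participant random intercept and a group-by-time test (five equal bands, the only shape run), power at equal size is .425 at r = .5 and .579 at r = .7. The covariate model gives .524 and .662, about 10 and 8 points more.

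**6. Alcohol instrument.** No arithmetic applies. The objectives and the analysis text say AUDIT, with four bands; the RCT list and the upload say AUDIT-C. Nothing states how AUDIT-C scores would fall into four bands.

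**The case against.** The strongest reply is that the ordered-logit sentence is not a full model statement. It does not name the treatment indicator or a time term either, so silence about TP1 is weak evidence that TP1 will be left out. The aim of assessing change, and the listing of TP1 among the time points, suggest that it will be used somehow. This stands: a reader might infer that the plan discards baseline, and the text does not support that. It supports only that the use of TP1 is unspecified, and that the one route stated for adding a covariate depends on chance imbalance.

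The plan's caution about the number of covariates in a small sample also stands, and it is a real cost. So does the point that the gains rest on borrowed inputs. Floor effects are plausible on the DAST 10 and alcohol scales, because participants are expected to be severe on at least one measure, not on all. With an assumed 80% in the lowest band at r = .5, the gain at equal size falls to about 2 points (.21 v .23).

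The analyses are exploratory and the pilot's main goal is feasibility. That limits the priority of the point but does not favour omitting TP1; no scenario run did.

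On alcohol, AUDIT may be shorthand for AUDIT-C; the plan is loose with other scale names. Nothing confirms this, though, and the documents give no scoring for either form. A reader might conclude that the four bands are wrong for the form in use; the documents do not go that far.

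**Conclusion.** The point holds as a cheap improvement, not as an error. The symptom-band models do not name the TP1 score, the functioning models do adjust for baseline, and the imbalance rule is no substitute.

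Two stronger readings fail. First, the .80 power is not affected: it belongs to the baseline-adjusted ANCOVA and reproduces. Second, the symptom comparisons are not biased by the omission: under randomisation, what is lost is precision.

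At equal type I error the gain from naming TP1 is about 1 to 2 points at r = .3, 4 to 7 at r = .5 and 13 to 22 at r = .7, and smaller under a heavy floor. These figures assume 19 per arm, d = .65, two-sided .05 and the band shapes listed. They show direction and rough size only. The case does not rest on any one of them, because the TP1 score is already collected.

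The AUDIT and AUDIT-C mismatch is a separate inconsistency that needs no power assumption.

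**What to change.** 1. In the Aim 3 secondary and exploratory analyses, include the TP1 score of the same measure as a covariate in each ordered-logit model, beside treatment and the random provider effect. State how the two follow-ups are handled: either separate models at TP3 and TP4, or one joint model with a participant random effect and a contrast at each time.
2. Analyse the pooled z-score with the baseline-adjusted linear mixed ANCOVA of hypothesis 3b, using the TP1 pooled z-score as covariate.
3. Reconcile AUDIT with AUDIT-C across the objectives, the analysis text and the questionnaire lists, and state the banding for the form actually given.
4. Leave the PCL-5 10-point model as written, since it already uses TP1, and keep the exploratory label.

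The cost is wording only; no new data or visits are needed. The downsides are one more parameter in a small sample, a likelihood-ratio type I error of about .06 to .08, and an odds ratio that becomes conditional on the TP1 score, which the report should say.
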